Upon signing informed consent, patients will undergo Screening assessments at the study center, as per the Schedule of Events ([Table 2](#)). Within each cohort, patients who are determined to be eligible will be randomized that same day (Day 1) in a 1:1 ratio to receive either NasoVAX or placebo with approximately 10 and 14 patients in Cohorts 1 and 2, respectively, receiving NasoVAX and 10 and 14 receiving placebo in Cohorts 1 and 2, respectively ([Table 1](#)). Approximately 24 patients will receive NasoVAX and 24 will receive placebo in Cohort 3. Randomization in Cohort 2 will be stratified by age groups of 35-64 years and 65 years and above. Randomization in Cohort 3 will be stratified by age groups (ages 35-64 years, ages 65 and above) and co-morbidity (one or more risk factors present, no risk factors present). Enrollment of patients ages 35-49 will not exceed approximately 30% of the randomized population of either treatment arm.

Table 1 Study Design

Cohort	Cohort Description	Number of Doses	NasoVAX Dose (vp)	Number of patients	
				NasoVAX	Placebo
1	Ages 35-49 years and risk factors disallowed	Single	1 x 10 ¹¹	10	10
2	Ages 35 and above and risk factors disallowed	Single	1 x 10 ¹¹	14	14
3	Ages 35 and above and risk factors allowed	Single	1 x 10 ¹¹	24	24
Group Total				48	48
Study Total				96	

Study drug will be administered as a single intranasal dose of 0.5 mL (0.25 mL each nostril) in the supine position after which patients must remain in the supine position for 30 minutes. Patients will be observed for at least 2 hours post intranasal administration. Patients who are randomized will be considered enrolled in the study.

No in-person visits are expected during the study after Day 1 unless a participant experiences a change in symptoms or AE that requires a visit for assessment.

Prior to discharge from the study center on Day 1, patients will be provided with:

- A fingertip pulse oximetry device that connects to a mobile device connecting to a tablet that will be supplied to the patient to measure resting SpO₂ and resting pulse rate remotely. Patients will be trained on the use of the device and tablet.
- A digital thermometer for measurement of oral temperature
- Instructions regarding how to take the above measurements and access and complete a web-based electronic diary (eDiary)

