7.1.3 Serious Adverse Event

An AE or suspected adverse reaction is considered serious (an SAE) if, in the view of either the Investigator or Sponsor, it results in any of the following outcomes:

- Death
- Life-threatening (An AE is considered life-threatening if, in the view of either the Investigator or Sponsor, its occurrence places the patient or subject at immediate risk of death. It does not include an AE that, had it occurred in a more severe form, might have caused death.)
- Inpatient hospitalization or prolongation of existing hospitalization
- A persistent or significant incapacity or substantial disruption of the ability to conduct normal life functions
- A congenital anomaly/birth defect

Life-threatening means that the patient or subject was at immediate risk of death at the time of the SAE; it does not refer to a serious AE that hypothetically might have caused death if it were more severe. Hospitalization does not include same day surgery, elective surgery, optional admission not associated with a precipitating AE (ie, elective cosmetic surgery), or hospitalization planned before the start of the study for a pre-existing condition that has not worsened. Persistent or significant disability or incapacity means that there is a substantial disruption of a person's ability to carry out normal life functions.

Important medical events that may not result in death, be life-threatening, or require hospitalization may be considered serious when, based upon appropriate medical judgment, they may jeopardize the patient or subject and may require medical or surgical intervention to prevent one of the outcomes listed in this definition. Examples of such medical events include allergic bronchospasm requiring intensive treatment in an emergency room or at home, blood dyscrasias or convulsions that do not result in inpatient hospitalization, or the development of drug dependency or drug abuse.

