7.6.2 Special Reporting Situations

Hospitalization or Death

Hospitalization and death are outcomes of an event. The event that resulted in hospitalization or death should be recorded and reported on the SAE form and the AE eCRF page.

As noted in Protocol Section 9.2 and Section 8.2.6, hospitalizations and deaths related to worsening fever, cough, shortness of breath, resting SpO₂ or resting pulse rate or symptoms of COVID-19 at Screening will not be considered SAE, although narratives of the hospitalizations and causes of death will be reported to and reviewed by the DMC in real time.

Surgical or Diagnostic Procedures

The illness leading to a surgical or diagnostic procedure is to be recorded as an AE/SAE, not the procedure itself. The procedure is to be captured in the case narrative as part of the action taken in response to the illness.

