9.10 Analysis of Safety Data

Quantitative safety data, including the frequencies of AEs, oral temperatures, use of antipyretics and bronchodilators, and length of hospital and ICU stay, will be summarized using descriptive statistics and frequency distributions. Qualitative safety data will be summarized by frequencies and percentages. All summaries will be presented by overall NasoVAX, NasoVAX cohort, and pooled placebo groups. AEs will be coded using the latest version of MedDRA, and severity will be coded using the latest version of the CTCAE, v.4.0.3. Concomitant medications will be coded using the latest version of the World Health Organization (WHO) drug dictionary. Safety comparisons will be made by treatment group and include comparisons for cohort or stratification factors (ages 35-64 years vs. ages 65 years and above, one or more risk factors present vs. no risk factors present).

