9.10.1 Adverse Events

All AEs recorded on the AE eCRF during the study will be coded to SOC and PT using the most current version of MedDRA, currently MedDRA 20.1.

A treatment-emergent AE (TEAE) is defined as an AE that was not present prior to treatment with IP, but appeared following treatment or was present at treatment initiation but worsened during treatment. An AE that was present at treatment initiation but resolved and then reappeared while the patient was on treatment is a TEAE (regardless of the intensity of the AE when the treatment was initiated). Programmatically, an AE will be classified as a TEAE if the start date and time occurs on or after the start date and time of first IP dosing.

All reported AEs will be listed, but only TEAEs will be summarized.

The overall incidence of TEAEs (number and percentage of patients, 95% CI) as well as the number of events will be summarized by treatment group, intensity as assessed by the latest version of National Cancer Institute's Common Terminology Criteria for AEs, SAE, related TEAE, TEAEs leading to study or investigational product discontinuation, and SAEs resulting in death.

The number (percentage, 95% CI) of patients with AEs from Day 1 to Day 42 (including SAEs) will be summarized for each MedDRA system organ class and PT and by treatment group. The number (percentage) of patients with SAEs from Day 1 to Day 210 will be summarized in a similar fashion. The number (percentage, 95% CI) of patients with AEs by severity and by relationship to IP will also be summarized.

The TEAEs will be summarized and tabulated at both the patient (n [%] of patients) and event (number of events) level for each treatment group and overall as follows:

- SOC and PT
- SOC, PT, and maximum reported severity
- SOC, PT, and maximum relationship to investigational product

Subjects with SAEs will also be summarized by SOC and PT for each treatment group and overall.

For the incidence at the patient level by SOC and PT, if a patient experiences more than 1 event within the same SOC and PT, only one occurrence will be included in the incidence.

For the incidence at the patient level by SOC, PT, and severity, if a patient experiences more than 1 event within the same SOC and PT, only the most severe occurrence will be included in the incidence.

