9.10.2 COVID-19 Symptoms

Each patient will record the following COVID-19 symptoms daily in the eDiary with the study-supplied devices (ie, tabloid, digital thermometer) through Day 14. For patients who are unable to complete the eDiary, the records of symptoms will be collected over the telephone.

- fatigue, chills, headache, cough (with or without sputum production), myalgia, sore throat, shortness of breath, nasal congestion, diarrhea, nausea or vomiting, and oral temperature.

The patient will be asked to grade the symptoms in scale of “not at all”, “a little bit”, “somewhat”, “quite a bit”, and “very much”.

A cumulative summary of the number and percentage of patients experiencing at least one symptom (as local, systemic, and overall) through Day 14 will be tabulated by maximum severity and treatment group. Differences between each NasoVAX cohort and pooled placebo for cumulative events (local, systemic, and overall) will be tested using Kruskal-Wallis tests. The number and percentage of subjects experiencing at least one grade of “quite a bit” and “very much” symptom through Day 14 days for each symptom type, as well as 95% Clopper Pearson exact CIs, will be presented by treatment group.

A summary of the number and percentage of subjects experiencing at least one event through Day 14 will also be tabulated by event type, maximum severity, and treatment group. In addition, a descriptive summary of the duration of events (regardless of severity) will be tabulated by event and dose group.

Generally, symptoms recorded in the eDiary and (unsolicited) AEs recorded in the AE log will be summarized separately. A change in symptoms from baseline will not be recorded as an (unsolicited) AE unless it meets the criteria of an SAE. Any event found in the AE log that is also captured in the eDiary will not be counted as an AE to avoid duplication.

9.10.3 *Safety Laboratory Tests and Vital Signs*

Clinical laboratory results will be listed for urinalysis. Presentations will use SI Units.

Observed and change from baseline of continuous clinical laboratory values will be summarized descriptively by each treatment group and visit. Summary statistics for continuous parameters will be presented by treatment group as follows: pre-treatment, post-treatment, and change from pre-treatment to post-treatment assessment.

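### SAP 9.10.2 keeps symptom changes that qualify as SAEs as adverse events, then excludes every logged event also in the eDiary from the AE counts, with no exception for serious events

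*SAP*

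**What the plan says.** SAP 9.10.2 (COVID-19 Symptoms) covers the daily eDiary, which has ten symptom items plus oral temperature and runs through Day 14. It says diary symptoms and unsolicited AEs are in general summarized separately. Two rules follow, one directly after the other:

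- On recording: "A change in symptoms from baseline will not be recorded as an (unsolicited) AE unless it meets the criteria of an SAE".
- On counting: "Any event found in the AE log that is also captured in the eDiary will not be counted as an AE to avoid duplication".

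The SAP does not define what makes a logged event captured in the diary.

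SAP 9.10.1 (Adverse Events) plans the AE tables without mentioning the diary. TEAEs are tabulated by system organ class and preferred term, by maximum severity and by maximum relationship. It also says "The number (percentage, 95% CI) of patients with AEs by severity and by relationship to IP will also be summarized" and "Subjects with SAEs will also be summarized by SOC and PT for each treatment group and overall". Its Day 1 to Day 42 summary of AEs is stated to include SAEs. All reported AEs are listed, and AE and SAE listings are provided.

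Two other SAP sections bear on scope. SAP 7.2 and 7.6.2 take certain COVID-19 events out of SAE reporting, with 7.6.2 referring to "hospitalizations and deaths related to worsening fever, cough, shortness of breath" and the related signs and symptoms. SAP 7.1.1, which follows Protocol 9.1.1, keeps worsening of named COVID-19 signs, and of symptoms reported in the diary during Screening, out of AE reporting.

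**The concern.** The two rules in SAP 9.10.2 give opposite results for the same event. If sites follow the first, the diary-type symptom changes that properly reach the AE log are the serious ones. The second then says that events of this kind, once in the diary, are not counted. Taken at its word, it removes what the first was written to keep.

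AE incidence and severity is the first safety endpoint in SAP 3.3, and SAP 9.4 names initial safety as a purpose of the trial. Two programmers working from the same data could produce different SAE, TEAE, severity and relatedness tables for serious diary-symptom events, depending on which sentence they applied. The diary tables would not make good the loss. They rest on a five-step patient rating (SAP 6.2.2), whereas seriousness, causality and the investigator's severity grade belong to the AE record (SAP 7.2 and 7.3).

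**Working it through.** The plan states no figure on this point and no arithmetic applies. The check is to follow one type of event through the SAP.

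1. **Take a hypothetical event.** A patient without vomiting at Screening develops it within the 14 days, and the investigator judges it serious by a route other than hospitalization or death. SAP 7.1.3 allows this where the event could endanger the patient and need intervention to prevent a listed outcome: "Important medical events that may not result in death, be life-threatening, or require hospitalization may be considered serious when, based upon appropriate medical judgment". Life-threatening events and incapacity are further routes.

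2. **Is it in the diary?** Yes, in the ordinary case. Nausea or vomiting is a diary item (SAP 6.2.2). The diary and the AE reporting period both run through Day 14 or hospitalization (SAP 4.1 and 6.3.4).

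3. **Is it recorded as an AE?** Under the first rule of SAP 9.10.2, yes, because it meets the SAE condition.

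4. **Is it counted as an AE?** Under the second rule, no. That sentence covers any event in both sources and has no qualifier for seriousness.

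5. **Is it in the SAE and TEAE tables?** Under SAP 9.10.1, yes. It began after dosing, so it is treatment-emergent, and the SAE table by organ class and term states no exclusion.

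Steps 4 and 5 cannot both be applied, and step 4 defeats the purpose of step 3. SAP 9.13 does not settle the matter, because it ranks the SAP against the protocol and does not address a conflict inside the SAP.

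**How far this reaches**

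- Hospitalizations and deaths from the named COVID-19 signs, or from symptoms reported at Baseline (SAP 7.2) or Screening (SAP 7.6.2), are already exempt from SAE status. The exemption does not extend to the other seriousness routes in step 1.
- SAP 7.6.1 asks for a diagnosis rather than component symptoms, so many serious events would be logged under a term that is not a diary item.
- Listings are unaffected. Only counts change.

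**A related gap.** For a symptom absent at Screening that appears after dosing, SAP 9.10.2 treats it as a change from baseline, hence not an AE unless serious. SAP 7.1.1 ties its exemption to symptoms reported in the diary during Screening. The diary is completed at Screening and its scale includes a rating for no symptom at all, so it is unclear whether an absent symptom counts as reported. The two sections need the same answer.

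**The case against.** The best defence is that the two sentences belong together. The first sets the SAE exception. The second gives its purpose as avoiding duplication, and can be read as tidying up symptom entries that should not have been logged. An SAE record holds seriousness and causality that the diary lacks, so counting it duplicates nothing, and SAP 9.10.1 plans an SAE table without any diary exclusion. This may well be what was intended. It is not what the text says: one sentence is about recording and the other about counting, and the second applies to any event without qualification.

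A reader might infer that the rule is also inconsistent for non-serious events rated possibly or probably related, such as new nasal congestion after an intranasal dose. The documents do not support that. For non-serious events, related or not, both sentences of SAP 9.10.2 agree that the event is not an AE. Reporting such symptoms through the diary is a deliberate and defensible choice. A request to count them, or to show AE tables with and without them, would be a preference and not the correction of an error.

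The objection that few events are affected also stands, and it limits the weight of the point.

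**Conclusion.** The point holds for serious events. Followed literally, the de-duplication sentence in SAP 9.10.2 drops serious diary-symptom events that the sentence before it keeps, and it conflicts with the summaries planned in SAP 9.10.1. This is a contradiction between stated rules, more than a missing detail, and it should be corrected before the tables are programmed.

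The scope is narrow. The number of patients affected cannot be estimated, because the documents give no rate for serious symptom events outside the existing exemptions. The conclusion assumes that at least some such events are logged under a diary term.

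A reader might also infer that safety oversight during the trial is weakened, or that serious events vanish from the report. Neither follows. The rule is not stated to govern data monitoring committee review or the stopping rules, and every AE and SAE remains in the listings. The wording of the causality categories in Protocol 9.3.2 and SAP 7.3.2 is a separate question on which nothing here depends.

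**What to change.** - Amend the second rule in SAP 9.10.2 so that de-duplication applies only to non-serious events. State that any AE-log event meeting SAE criteria is always counted in the AE, TEAE, severity, relatedness and SAE tables.
- Define overlap in the same place, for example the same symptom, overlapping dates, and a diary rating above the lowest step.
- Align SAP 7.1.1 with SAP 9.10.2 on symptoms absent at Screening that appear after dosing, and check the wording against Protocol 9.1.1 and the TEAE definition in SAP 9.10.1.
- Optionally, flag non-serious overlapping events rated possibly or probably related, so that they can be found in the listings.

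The cost is one amended sentence with a short definition, one clarifying sentence and, if wanted, one flag variable. Protocol 10.4 has the SAP finalized before database lock and unblinding, which is the time to make the change. The downside is that a few serious symptoms will appear in both the AE and the eDiary tables, which a footnote can explain.

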9.11 Basic Analyses

9.11.1 *Physical Examinations*

Physical exam results will be listed including specification of any abnormalities observed.

9.11.2 *Prior and Concomitant Medications*

Prior and concomitant medications will be summarized by the latest version of WHO Drug Dictionary Anatomical Therapeutic Chemical (ATC) level 3 and PT. If a medication has no ATC Level 3 code, then ATC Level 2 will be used instead. The total number of concomitant medications and the number and percentages of patients with at least 1 concomitant medication will be summarized by treatment group/cohort for the Safety Population. Placebo will be the collective (pooled) across treatment groups.

Concomitant medications that were started prior to study treatment will be summarized similarly. Prior medications that are not concomitant will be listed but not tabulated.

9.12 General Conventions for Tables, Listings and Figures

For summary tables, unless otherwise specified, the number of decimal places provided in the SAS output will be based on the accuracy of the least accurate value in the raw data as follows:

n	integer
Arithmetic mean	1 decimal place more than the least accurate number in the raw data
SD	2 decimal places more than the least accurate number in the raw data
Geometric mean	1 decimal place more than the least accurate number in the raw data
Median	1 decimal place more than the least accurate number in the raw data
Minimum	same number of decimal places as raw data
Maximum	same number of decimal places as raw data
Confidence interval	same number of decimals as the associated statistic
Geometric mean ratio	2 decimal places

9.13 Conflicts and Deviations

In the event of a conflict between the SAP and study protocol, the SAP will supersede.

Any deviation from the original statistical analysis plan will be described and justified in the final clinical study report.

